### 8.2. Sample size justification

Data from a minimum of 200 subjects will be evaluated. A minimum of 100 subjects will be evaluated for each main location of surgery (abdominal and peripheral).

---

**PROTOCOL** 2020-PMC-01  
**TITLE:** Safety and Performance of POLYMAILLE® C vascular prosthesis  
**EFFECTIVE DATE:** 15 January 2021

---

The number of patients has been chosen in accordance with the realistic number of operated patients in the involved hospitals.

---

PROTOCOL	2020-PMC-01
TITLE:	Safety and Performance of POLYMAILLE® C vascular prosthesis
EFFECTIVE DATE:	15 January 2021

---

## 9. DATA MANAGEMENT

### 9.1. Data sources

Real World Data sources used to generate Real World Evidence are:

- Data derived from Electronic health Record
- Medical claims and/or billing data
- Product and/or disease registry data

### 9.2. Data to collect

As mentioned previously considering study is retrospective and considering that every site can have different ways to follow their patients after surgery, data will be collected as much as possible in order to determine the clinical safety and effectiveness.

The following data will be collected, when available according to participating site available data.

- **Identification and demographic data**
  - Patient identification
  - Indication and location of the treatment
  - Location of the surgery
  - Patients demographics
    - Date of birth
    - Sex
    - Mass
  - Identification of implanting physician
  - Name of the institution
- **Pre-operative data**
  - Risks factors, such as hypertension, diabetes, coronary artery disease, hyperlipidemia, tobacco use, obesity, anaesthesia risk and any cardiovascular risk factor.
  - Summary of previous vascular interventions at the same or other relevant vascular sites, including non-surgical interventions and previously implanted vascular devices (e.g. stents, endovascular prostheses, surgically placed vascular grafts)
  - Relevant medications
  - Diagnostic criteria
    - Clinical assessment (e.g. non-invasive hemodynamic assessment);

---

PROTOCOL	2020-PMC-01
TITLE:	Safety and Performance of POLYMAILLE® C vascular prosthesis
EFFECTIVE DATE:	15 January 2021

---

- Objective assessment (e.g. C.T. scanning, magnetic resonance imaging, ultrasonography, arteriography, duplex Doppler)

- **Operative data**

- Date of procedure
- Identification data for the vascular prosthesis including configuration (e.g. straight uniform or bifurcated) and diameter
- Information regarding the procedure:
  - Identity of native vessel treated
  - Details of anastomoses (e.g. type (end-to-end), location
  - Length of prosthesis implanted (if available)
  - Adjunctive vascular procedures
- Relevant medication (e.g. heparin, other anticoagulants)
- Assessment of prosthesis function and mode of assessment if available (e.g. intraoperative angiography, intraoperative Doppler)
- Failure modes and adverse operative events

- **Post-operative data**

- Interval of follow-up (e.g. discharge or 7 d to 14 d after surgery, 30 days, 6 and 12 months after surgery, up to 5 years for exploratory time points)
- Date of follow-up visits
- Summary of vascular interventions, including minimally invasive procedures
- Clinical evaluation:
  - Clinical assessment (e.g. non-invasive hemodynamic assessment)
  - Objective assessment of prosthesis (e.g. C.T. scanning, magnetic resonance imaging, ultrasonography, arteriography, duplex Doppler)
- Relevant medications (e.g. anticoagulants or antiplatelets)
- Any documented adverse events including the events listed in section 6.2 anticipated risks and any events that lead to the patient's death

- **Any documented adverse events data**

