#### **5.3.1. Inclusion criteria**

Patients must meet all the following inclusion criteria in order to be eligible for inclusion in the study:

- Patient has a minimum of 1-year post-operative follow-up data available, or complete data to death

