## 7.1. Performance endpoints

- Primary performance endpoint is **primary patency rate at 1 year** after surgery using POLYMAILLE® C.
- The others performance endpoints are:
  - **Procedural success rate**, *defined as:*
    - *Ability to use with no need for replacement by another device and,*
    - *Effective vascular flow restoration after procedure and,*
    - *In case of aneurysm, exclusion of aneurysmal portion after procedure.*
  - **Primary patency rate**, *defined as rate of patent grafts without any procedure or intervention of the conduit itself*
  - **Primary assisted patency rate**, *defined as rate of patent grafts, with or without procedure or intervention of the conduit itself after device implantation, such as endovascular balloon angioplasty or anastomotic revision, however with graft never thrombosed (graft occlusion)*
  - **Secondary patency rate**, *defined as rate of patent grafts, with or without procedure or intervention of the conduit itself after device implantation, such as endovascular balloon angioplasty or anastomotic revision, lysis and/or thrombectomy.*
  - **Device Failure**, *defined as:*
    - *Uncontrolled blood leakage from device*
    - *Loss of structural integrity, e.g. rupture and/or exaggerated dilation (> 50 %)*
    - *Occlusion of the device*
    - *Total or partial replacement of the device required*

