## 8. STATISTICAL CONSIDERATIONS

### 8.1. Statistical design, method and analytical procedures

All the patients participating in the study who met the eligibility criteria will be included in the study population.

A descriptive analysis with clinical characteristics of all patients included in the study will be performed at the index date.

Exploratory analyses will be conducted globally and by the 2 sub-populations. Results will be stratified according to 2 main surgical locations:

- Abdominal surgical location:
  - Aorto-aortic and/or aorto-iliac and/or aorto-femoral repair
- Peripheral surgical location:
  - Peripheral artery repair and extra anatomic bypasses

Since no hypotheses will be tested, study objectives will be addressed using descriptive statistics only. Given the real-world nature of the data, the use of multiple imputation methods for missing data would introduce bias as missing data cannot be considered completely at random (MCAR) or at random (MAR). Variables will not be imputed, with the exception of dates in which the exact day is missing: the missing day will be replaced by the middle day of the month.

Continuous variables will be described with number of patients with valid / missing observations, mean and its 95% confidence interval (95%CI), standard deviation (SD), median, 25 and 75 percentiles (P25 and P75, respectively), minimum and maximum. For non-normally distributed continuous variables geometric mean and its 95%CI will be reported too.

For categorical variables counts and percentages per category will be presented. Missing observations (including invalid observations) will be tabulated as a separate category. If the % of missing data does not exceed 10 %, the calculation of proportions will not include the missing/invalid category in the denominators.

P-values will be presented in the summary tables, in association with the descriptive statistics. In addition, 95% confidence intervals (95%CI) will be presented when considered convenient or relevant. Results will be graphically represented when appropriate to make interpretation easier.

The two-sided level of significance will be set at 0.05 for all the statistical tests performed.

Statistical calculations will be carried out by using R software. More details on the statistical analysis will be provided in the Statistical Analysis Plan.

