### 9.4. Missing data

Some endpoints can be missing for some subjects. Endpoints proportions will be calculated on the number of non-missing observations. No imputation method is planned.

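### 1-year primary patency as a proportion of non-missing observations, under site-specific follow-up times, can be biased, most likely upward, because late visits settle successes but not undated failures

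*Protocol*

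**What the plan says.** - **Endpoint.** Protocol 7.1: "Primary performance endpoint is primary patency rate at 1 year after surgery". Primary patency is "defined as rate of patent grafts without any procedure or intervention of the conduit itself". It is a fixed-time rate, and once lost it cannot be regained.
- **Follow-up.** Protocol 9.2 says that "every site can have different ways to follow their patients after surgery". The time points are examples only: "Interval of follow-up (e.g. discharge or 7 d to 14 d after surgery, 30 days, 6 and 12 months after surgery".
- **Eligibility.** Protocol 5.3.1: "Patient has a minimum of 1-year post-operative follow-up data available, or complete data to death". A living subject may therefore have the first informative visit well after 1 year.
- **Denominator.** Protocol 9.4: "Endpoints proportions will be calculated on the number of non-missing observations. No imputation method is planned". Section 8.1 has a different rule: if missing data do not exceed 10%, "the calculation of proportions will not include the missing/invalid category in the denominators". By implication they stay in above 10%.
- **Missingness and dates.** Section 8.1 holds that missing data are neither MCAR nor MAR. Its only date rule puts a missing day at mid-month. Section 9.2 collects visit dates and, as far as available, adverse-event and explant dates. Graft stenosis/occlusion is a listed event in 6.2.

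**The concern.** Take two living subjects, both last seen with a patent graft at 6 months and next seen at 18 months. The first graft is patent and untreated at 18 months, so it was certainly primary patent at 1 year. The second is occluded at 18 months with no record of when, so its 1-year status is unknown. If status is worked out from whatever visits exist, the section 9.4 denominator keeps the first graft and loses the second. Whether a graft counts then depends on its outcome, even among subjects with complete follow-up.

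At stake is the primary performance endpoint of a study that section 5.2 says is needed to keep the device on the European market. The effect would vary with each site's visit pattern, and a larger sample would not remove it. Deaths and the type of evidence for patency are separate matters, not covered here.

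**Working it through.** The protocol gives no calculated figure to reproduce: section 8.2 sets at least 200 subjects (100 per location) on feasibility. The check is therefore of the bias in the complete-case proportion.

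**Notation.** S0, S12 and SL are true primary patency at the last visit before the gap, at 12 months and at the late visit. k is the share of all gap failures that are undated, that is, the share of patients with the gap times the share of their gap failures without a date. Neither factor is in the documents, so k is an assumption, shown from 0.25 (half × half) to 1.

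**Formulas.**
- Undated failures dropped: [S12 − k(S12 − SL)] / [1 − k(S0 − SL)]
- Share missing: k(S0 − SL)
- Bias if failures are dated at the detecting visit: +k(S0 − S12)
- Bias if undated failures stay in the denominator as non-successes: −k(S12 − SL)
- Dropping inflates only if (S12 − SL)/(S0 − SL) < S12.

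**Constant hazard (assumed), gap 6 to 18 months.**

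True 90%: S0 = 0.90^0.5 = 0.949, SL = 0.90^1.5 = 0.854. Condition: 0.046/0.095 = 0.49 < 0.90, so inflation.
- k = 0.25: 0.8885/0.9763 = 91.0%, **+1.0 point**, 2.4% missing
- k = 1: 0.8538/0.9051 = 94.3%, **+4.3 points**, 9.5% missing

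True 85%: S0 = 0.922, SL = 0.784.
- k = 0.5: 0.8168/0.9309 = 87.8%, +2.8 points, 6.9% missing
- k = 1: 0.7837/0.8617 = 90.9%, **+5.9 points**, 13.8% missing

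**Other handling of the same grafts.**
- Dated at detection, true 90%: +1.2 points (k = 0.25) to +4.9 (k = 1)
- Kept in the denominator, true 90%: −1.2 to −4.6 points
- Kept in the denominator, true 85%, k = 1: 78.4%, or −6.6 points. Here 13.8% are missing, above the 10% threshold of section 8.1, so 9.4 gives 90.9% and 8.1 by implication 78.4% on the same data.
- Only an assessment at 1 year counts, but failures known by 6 months stay in. True 90%, half the patients without a 1-year visit: 0.45/(0.5 + 0.5 × 0.0513) = 85.6%, or −4.4 points.

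**Curves quoted in section 5.1 (6/12/24 months), 18-month value interpolated.**
- ePTFE 95/91/76%, SL = 83.5%: k = 0.25 gives 0.8912/0.9712 = 91.8% (+0.8); k = 1 gives 0.835/0.885 = 94.4% (+3.4)
- Study device 95/95/86%, SL = 90.5%: k = 0.25 gives 94.9% (−0.1); k = 1 gives 0.905/0.955 = 94.8% (−0.2). The condition fails because 0.045/0.045 = 1 > 0.95.

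**Scale.** The Wilson 95% interval at 90% is 85.1–93.4% for n = 200 and 82.6–94.5% for n = 100.

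**The case against.** A reader might infer that the protocol inflates 1-year patency by construction. The documents do not support that, for four reasons.

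1. Section 9.4 does not say that a late patent finding is carried back to 1 year, or that a late-found failure is set to missing. Such rules may sit in the SAP, which is not shown, and their absence from the protocol is not criticised. This stands. But the other readings do not rescue the proportion: dating at detection overstates patency, and counting only a 1-year assessment can understate it.
2. Many failures will have dates. Re-interventions and explants usually carry one, and event dates are collected where available. This stands, and it shrinks k. At k = 0.25 and true 90% the bias is 1 point, small against the confidence interval.
3. The sign is not fixed. The study device's own curve gives about zero. This stands, though that arm had 22 grafts in one above-knee indication. No loss among about 21 grafts between 6 and 12 months is compatible with a loss of up to 1 − 0.05^(1/21) = 13% (one-sided 95%), and section 5.2 says evidence is lacking for abdominal sites.
4. The largest figure meets the 10% rule of section 8.1. This stands for the 13.8% case. The true-90% scenarios stay below 10%, where 8.1 and 9.4 both exclude the missing.

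An interval-censored estimator is also no cure-all. If every visit fell at 6 and 18 months and no failure were dated, it would not be unique at 1 year. It further assumes visit times unrelated to outcome, which is doubtful in routine records.

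**Conclusion.** The point holds in conditional form. The protocol fixes a complete-case proportion at 1 year although follow-up times differ by site and it regards missingness as non-random. If undated, late-found failures are dropped, or dated at detection, 1-year primary patency is likely overstated. When they are dropped, the assumed constant hazard and 6–18 month gap give about +1 point under moderate assumptions and +4 to +6 points when every patient has the gap and no failure is dated. The upper end is a limiting case, not an expectation. The true size cannot be known from the documents. It is near zero on the device curve in section 5.1 and negative if missing cases remain in the denominator. The two denominator rules can by themselves move the result from 90.9% to 78.4% in the 13.8%-missing example. The study is descriptive and tests no hypothesis, so this affects the accuracy of the reported rate rather than a test decision. It should be corrected before analysis.

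**What to change.** - In 9.4, state that the patency endpoints are estimated as time to loss of patency. Use the recorded event or intervention date where there is one, and otherwise the interval from last known patent to first known lost. Apply an interval-censored (Turnbull) method, read at 1 year for the primary endpoint.
- Where the estimate is not unique at 1 year, report its bounds. In the extreme true-85% case above they would be 78.4% and 92.2% (SL and S0). Varied visit times and dated failures narrow them.
- Keep the fixed-time proportion as supportive, with undeterminable grafts counted first all as lost and then all as patent. At true 90% these limits are 88.8% and 91.2% for k = 0.25, and 85.4% and 94.9% for k = 1.
- Reconcile 8.1 with 9.4 so that one denominator rule governs the endpoints at every level of missingness.

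The cost is wording in 8.1, 9.4 and the SAP. Visit dates are already to be collected, and event dates as far as available. The downside is a less familiar estimator and a 1-year figure that may be slightly less favourable.

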**As far as available the following data will be collected per adverse event:**

- Type of event, date of occurrence, severity, management (e.g. none, medical treatment, endovascular procedure, open surgery), outcome (e.g. continuing, resolved, unknown, death)

---

PROTOCOL	2020-PMC-01
TITLE:	Safety and Performance of POLYMAILLE® C vascular prosthesis
EFFECTIVE DATE:	15 January 2021

---

- Any Documentation of prosthesis involvement
- Any Documentation of probable causative factors (e.g. caused by the prosthesis, patient factors, technical factors)
- Explant data:
  - Date
  - Whether the subject is living or deceased
  - Reason for explant, if applicable
  - Relevant observations (e.g. device integrity, device positioning, tissue incorporation, vascular tissue erosion), if available

A separate document with all available data to collect will be produced in a second time to add further details depending on the level of details available.

### 9.3. Data consistency

Data consistency will be verified for each variable. Harmonization of units (conversion), categorical variables consistency and ranges of numerical variables will be also verified. This step will be proceeded before database freezing and analyses. If inconsistencies are noticed, monitoring and checks will be asked from the sites.

### 9.4. Missing data

Some endpoints can be missing for some subjects. Endpoints proportions will be calculated on the number of non-missing observations. No imputation method is planned.

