## 2. SYNOPSIS

Title:	A Retrospective, Observational, Multicentre Study to Collect Clinical Safety and Performance data on POLYMAILLE® C vascular prosthesis
Study Population:	Subjects who did receive POLYMAILLE® C at least one year ago for replacement or bypass of arteries. 2 main sub-populations will be studied depending on location of surgery (abdominal and peripheral), but data will be collected for all subjects who did receive POLYMAILLE® C.
Study Design:	Multi-center retrospective case series
Study Type:	PMCF
Number of subjects:	Data from a minimum of 200 subjects will be evaluated. A minimum of 100 subjects will be evaluated for each main location of surgery (abdominal and peripheral).
Follow-up	At least 1 year follow-up after surgery until a maximum of 5 years.
Study Product:	POLYMAILLE® C vascular prosthesis
Intended use:	POLYMAILLE® C vascular prostheses are indicated for replacement or bypass of arteries presenting aneurysm or obliterative arterial disease. Their indication is restricted to abdominal and peripheral surgery not crossing the knee flexion crease.
Objectives:	Describe safety and performance of POLYMAILLE® C
Performance primary endpoint:	Primary patency rate at 1 year after surgery using POLYMAILLE® C
Safety primary endpoint:	Mortality rate at 30 days after surgery using POLYMAILLE® C
Performance secondary endpoints:	
 
• Procedural success rate
 
• Primary patency rate at 30 days and 6 months after surgery using POLYMAILLE® C
 
• Primary assisted patency rate at 30 days, 6 months and 1 year after surgery using POLYMAILLE® C
 
• Secondary patency rate at 30 days, 6 months and 1 year after surgery using POLYMAILLE® C
 
• Device failure during procedure or at discharge, at 30 days, 6 months and 1 year after surgery using POLYMAILLE® C
 

PROTOCOL	2020-PMC-01
TITLE:	Safety and Performance of POLYMAILLE® C vascular prosthesis
EFFECTIVE DATE:	15 January 2021

Safety secondary endpoints	
 
• Mortality rate during procedure or at discharge, at 6 months and 1 year after surgery using POLYMAILLE® C
 
• Limb salvage rate at 30 days, 6 months and 1 year after surgery using POLYMAILLE® C
 
• Adverse event during procedure or at discharge, at 30 days, 6 months and 1 year after surgery using POLYMAILLE® C
 

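### Subjects who die before 1 year are enrolled by design, but the plan does not say how they enter the 1-year primary patency rate, and the denominator rules in 9.4 and 8.1 give different answers

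*Protocol*

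**What the plan says.** - **Eligibility.** Protocol 5.3.1 requires: "Patient has a minimum of 1-year post-operative follow-up data available, or complete data to death". Early deaths are therefore enrolled on purpose, and 8.1 keeps them in the analysis: "All the patients participating in the study who met the eligibility criteria will be included in the study population".
- **Endpoint.** The synopsis names the primary performance endpoint as "Primary patency rate at 1 year after surgery using POLYMAILLE® C". Section 7.1 defines primary patency as "rate of patent grafts without any procedure or intervention of the conduit itself". It gives no denominator and no rule for death.
- **Denominator in 9.4.** "Endpoints proportions will be calculated on the number of non-missing observations", followed by "No imputation method is planned".
- **Denominator in 8.1.** For categorical variables: "If the % of missing data does not exceed 10 %, the calculation of proportions will not include the missing/invalid category in the denominators". By implication, the missing category stays in the denominator above 10%. Section 8.1 also rejects both MCAR and MAR for the missing data.
- **Data.** Section 9.2 collects, where available, the procedure date, follow-up visit dates, vascular interventions, and the date and outcome of each adverse event.

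**The concern.** Loss of primary patency is permanent: under 7.1 a conduit that has been re-treated cannot regain it. A subject whose graft occludes at month 2 and who dies at month 4 is eligible and has a known outcome, yet has no 1-year assessment. A subject who dies at month 4 with a patent graft contributes four months of known patency and also has no 1-year assessment. The text does not say whether either of them counts as observed, as missing or as something else.

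The study is descriptive, so the reported rate is the result. If two analysts can derive different primary rates from the same charts, the main figure is not fixed. If deaths are simply dropped, the cohort shrinks between time points and primary patency could appear to rise, which is impossible in a fixed cohort.

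**Working it through.** The protocol gives no expected patency, mortality or precision, and its sample size rests on feasibility (8.2), so there is no figure to reproduce. The check takes one location at its minimum of n = 100 (8.2).

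**Inputs**
- d = deaths before 1 year. Assumed, 5 to 15 per 100.
- fs = share of 1-year survivors who lost primary patency. Assumed, 5% to 20%. The low end matches the 95% at 12 months in the Dacron arm of the randomised trial summarised in 5.1.
- fd = share of the deceased who lost patency before death. Assumed, 20% to 40%.

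**Estimates**
- A, 9.4 with every death missing: 1 − fs.
- B, 9.4 with failures before death counted and only patent-graft deaths dropped: (n − d)(1 − fs) / [(n − d) + d·fd].
- C, 1 minus the cumulative incidence of patency loss, with all implanted subjects in the denominator: 1 − [(n − d)fs + d·fd]/n.
- D, missing kept in the denominator, as 8.1 implies above 10%, with every death missing: (n − d)(1 − fs)/n.

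**Example: d = 10, fs = 5%, fd = 20%**
- A = 95.0%
- B = 85.5/(90 + 2) = 92.9%
- C = 1 − (4.5 + 2)/100 = 93.5%

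A is 1.5 points above C, and B is 0.6 points below it.

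**Error if all deaths are dropped.** A − C = (d/n)(fd − fs).
- Largest value in the ranges, d = 15, fs = 5%, fd = 40%: 0.15 × 0.35 = 5.25 points (95.0% against 89.75%).
- Smallest value, fd = fs = 20%: 0.
- Outside the ranges, d = 20, fs = 5%, fd = 40%: 0.20 × 0.35 = 7.0 points.
- Sign reversed, d = 10, fs = 10%, fd = 5%: 0.10 × (−0.05) = −0.5 points (90.0% against 90.5%).

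**Error if only patent-graft deaths are dropped.** With m = d(1 − fd) such deaths, C − B = (m/n)(1 − B), which is positive whenever there are both patent-graft deaths and failures.
- d = 5, fs = 5%, fd = 40%: B = 90.25/97 = 93.04%, C = 93.25%, a gap of 0.2 points.
- d = 15, fs = 20%, fd = 20%: B = 68/88 = 77.3%, C = 80.0%, a gap of 2.7 points.

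**Effect of the 10% rule in 8.1, with every death missing and fs = 5%**
- 10 deaths: missing is exactly 10%, so A applies: 95.0%.
- 11 deaths: D applies: 89 × 0.95/100 = 84.55%. Section 9.4 would still give 95.0%.

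One more death moves the rate by 10.45 points.

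**Rise over time if all deaths are dropped.** Suppose 5 of 100 grafts fail by 30 days (95%), those 5 subjects die before 6 months and no other graft fails. Six-month primary patency is then 95/95 = 100%.

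**The case against.** A reader might infer that the plan discards known graft failures and reports patency among survivors. The documents do not establish this. Section 9.4 excludes missing observations but never says that a failure documented before death is missing at 1 year. Section 7.1 defines primary patency by the history of the conduit, so a graft that has been re-treated has a known status at every later time. Limb salvage in 7.2 is worded as freedom from amputation and device failure in 7.1 is a list of events. Both fit cumulative counting, so the concern is weaker there.

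Nor can one say that patency will be overstated at any level of missingness. Above 10% missing, 8.1 would pull the rate down instead. The direction also depends on fd exceeding fs, which the documents do not show, and early deaths have less time in which to lose patency. The little evidence in 5.1 (no 30-day deaths in the randomised trial, one cardiorespiratory death in the survey) does not show that deaths are enriched for failed grafts.

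Finally, time-to-event methods are ordinary SAP content, and 8.1 defers detail to a SAP that is not at hand. That stands as far as technique goes. But 9.4 already fixes a proportion of non-missing observations, so a time-to-event SAP would depart from the protocol. The open treatment of death and the 8.1/9.4 conflict remain under every reading.

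**Conclusion.** The point holds as an unresolved and internally conflicting rule for the primary performance endpoint; it does not prove a bias in one direction. Neither reading of 9.4 gives the 1-year patency of the implanted cohort. Dropping all deaths is 0 to 5.25 points too high under the assumed ranges and too low if failure is rarer among the deceased. Dropping only patent-graft deaths is about 0.2 to 2.7 points too low over the same ranges.

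These errors are measured against 1 minus cumulative incidence. They are not the effect of switching to Kaplan-Meier, which censors at death, is a different quantity and cannot exceed 1 minus cumulative incidence. For scale, the 95% Wilson interval at 95% patency with n = 100 is 88.8% to 97.8%. The errors of reading are mostly smaller than that sampling uncertainty, but they are systematic. The 10.45-point step at the 8.1 threshold is larger than the interval's distance on either side of 95%.

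**What to change.** 1. In 7.1 and 9.4, state that any documented loss of primary patency up to a time point counts as a failure at that and every later time point, whether or not the subject later dies or has a visit.
2. Apply the same carry-forward to assisted and secondary patency according to their own definitions (a graft that is reopened can still have secondary patency), and to limb salvage and device failure.
3. Replace the 1-year proportion of non-missing observations with a time-to-first-loss estimate from the index date. Follow subjects who die with a patent graft to death. Give the Kaplan-Meier estimate and, beside it, the cumulative incidence of patency loss with death as a competing event.
4. Report the number of deaths by each time point alongside the patency rates.
5. Reconcile 9.4 with the 10% rule in 8.1, so that one denominator rule governs any endpoint still reported as a proportion.

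The cost is protocol and SAP wording and a little more analysis. No new data items are needed, since the dates are already to be collected where available. The stated patency rate may be slightly less favourable.
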